## **D. TRACEABILITY**

The traceability of each implanted device is guaranteed by its batch number and reference number.

## **E. INTENDED OBJECTIVE OF THE DEVICE IN THE INVESTIGATION**

SAGITTA® EVL R rods were used as standard, in accordance with their intended use and within their indications and for their usual target population, see below.

## **F. POPULATIONS AND INDICATIONS, CONTRAINDICATIONS OF USE FOR WHICH THE DEVICE UNDER INVESTIGATION IS INTENDED**

### **i. INDICATED POPULATION(S) FOR THE DEVICE**

Patients intended for treatment with a SAGITTA® EVL R stem are mature skeletal adults with an extremely painful and/or disabled joint, resulting from the failure of a total anterior hip replacement, without gender restriction.

It should be noted that SAGITTA® EVL R rods are suitable for most femoral revision with bone defects (Paprosky type I to III and SOFCOT stage II to IV).

It should be noted that pregnant or breastfeeding women should not be treated with a total hip replacement.

### **ii. DIRECTIONS**

SAGITTA® EVL R rods are intended for use in the revision of the femoral part of a total hip replacement.

### **iii. CONTRAINDICATIONS**

The rods should not be implanted in patients with the following contraindications:

Acute or chronic conditions – local or systemic (heart disease, uncompensated diabetes, regular hemodialysis, decreased immune system defenses, etc.).

## **G. PREREQUISITES FOR USE**

### **i. EDUCATION AND EXPERIENCE NEEDED**

Not applicable, this is an ambispective data collection, as the subjects have already been implanted with the device under investigation.

Only patient follow-up should be carried out by an orthopedic surgeon with knowledge of anatomy, biomechanics and reconstruction surgery of the musculoskeletal system, and previously trained in good clinical practices.

Considering the large number of SAGITTA® EVL R rod insertions performed in the prospective center and the experience of the surgeon who installs the SAGITTA® EVL R rods, no learning curve - including retrospective - is envisaged.

## ii. APPLICATION-SPECIFIC PROCEDURES

Not applicable, this is an ambispective data collection, as the subjects have already been implanted with the device under investigation.

Only prospective follow-up of patients will be carried out in accordance with the usual practice of the orthopaedic surgery and traumatology department in question.

## 3. CI DESIGN RATIONALE

### A. EVALUATION OF THE RESULTS OF THE RELEVANT PRECLINICAL EVALUATION

#### PERFORMED TO JUSTIFY THE USE OF THE DEVICE ON HUMAN SUBJECTS

The clinical evaluation of the SAGITTA® EVL R rods and associated locking keys demonstrated their compliance with the essential requirements on safety, acceptability of the benefit/risk balance, clinical performance and acceptability of adverse events.

However, in consideration of the elements evaluated, a post-marketing clinical study is considered necessary in order to:

- Generate postoperative clinical data (state-of-the-art revision rate of 15.2% at 5 years / 20.8% at 10 years).
- To confirm the clinical benefits associated with the use of the rods and their performance.

### B. EVALUATION OF CLINICAL DATA RELATED TO THE PROPOSED HF

The purpose of this IC is therefore to collect clinical data concerning the SAGITTA® EVL R rods as well as the CLV keys. EVLs, used for their intended purpose. These data will support and confirm the clinical evaluation of the device as agreed in the post-market surveillance plan implemented by SERF.

This data will complement the data already available regarding the performance and safety of the implant, in order to support compliance with Regulation (EU) 2017/745.

### C. CLINICAL DEVELOPMENT STAGE

According to Annex I of ISO 14155:2020, this clinical investigation (CI) is part of the post-market development stage of the device and is therefore qualified as a post-market clinical investigation, observational and with an additional cumbersome or invasive procedure.

## 4. RISKS AND BENEFITS OF THE DEVICE AND THE CI

### A. EXPECTED CLINICAL BENEFITS

The expected clinical benefits or advantages of SAGITTA® EVL R rods are pain reduction and functional recovery of the hip joint.

## B. EXPECTED ADVERSE REACTIONS

Known side effects (or complications) related to the use of SAGITTA® EVL R rods or the surgery required for their implantation are identified in the device's instructions for use and listed below:

- Allergy to the various materials that make up the implant and/or surgical equipment, in particular to metal,
- Pseudarthrosis, osteolysis, loosening of the prosthesis,
- Instability, dislocation, insufficient range of motion,
- Deformation, cracking or breakage of a component,
- Bone fracture,
- Collapse, migration, shortening or lengthening of the operated limb,
- Infection, sepsis,
- Delayed healing,
- Local, transient or permanent nerve damage,
- Cardiovascular disorders (hematoma, deep vein thrombosis), pulmonary embolism,
- Urinary tract infection,
- Deep abscess, fistula,
- Deterioration of the femoral and acetabular implant by stem/acetabulum contact during movements of extreme amplitude, mechanical noise may be heard when walking,
- The friction of components with each other can generate wear debris, corrosion or the release of metal particles that can induce a local reaction of the tissues,
- Residual hip pain.

*Notes:*

*Some of these complications can lead to prolonged operating time, revision surgery, or implantation failure/postponement of surgery.*

*It should be noted that any joint prosthesis is subject to wear and tear that can force the surgeon to operate again.*

*The surgeon is responsible for complications that may result from an incorrect prescription, a defective operating technique or a lack of asepsis. In no case can these complications be attributed to SERF.*

In addition, situations with an increased risk of failure are also listed:

- Severe muscular, neurological or vascular impairments affecting the affected extremity,
- Destruction, loss or poor bone quality that can affect the stability of the implant (for reasons of fatigue resistance), severe osteoporosis, significant deformities of the joint to be replaced,
- Any associated conditions that could compromise the function or implantation of the prosthesis,
- Systemic or metabolic disorders,
- Intellectual inability of patients to understand the surgeon's instructions,
- Drug addiction, alcohol, tobacco or drug abuse,
- Local bone tumors that may affect the stability of the implant,
- Obesity, overweight, high patient activities, intensive sports practices, patients with balance disorders,
- Bone loss or poor quality likely to affect the stability of the implant (for reasons of fatigue resistance, it is not recommended to use the "Sagitta EVL R" rod when this bone loss is greater than a height of 137 mm with respect to the center head),
- Pregnant or breastfeeding women.

## C. ASSOCIATED RESIDUAL RISKS AS IDENTIFIED IN THE RISK ANALYSIS REPORT

The risk management file for SAGITTA® EVL R rods and CLAV locking keys. EVL has been established in accordance with NF EN ISO 14971.

All risks associated with the design, manufacture, transport/storage, use and destruction of the device have been estimated. All residual risks were combined with each other after risk reduction to verify that a new risk was not generated.

Taking into account all the risk control actions put in place, the overall residual risk is considered acceptable.

The residual risks to the patient associated with the implantation of the rod are taken into account in the device's instructions for use, available in Appendix 2.

#### **D. RISKS ASSOCIATED WITH PARTICIPATION IN THE IC**

Subjects participating in the clinical investigation benefit from an operating procedure and medical follow-up identical to the procedure and care provided in routine practice. No additional procedures are performed during the implantation of the prostheses or during the follow-up of the subjects.

No specific risks associated with the participation of subjects in HF were identified.

#### **E. POSSIBLE INTERACTIONS WITH CONCOMITANT MEDICAL TREATMENTS**

No medical treatment is known to interfere with the expected results of SAGITTA® EVL R revision rod implantation.

#### **F. STUDIES UNDERTAKEN TO CONTROL OR MITIGATE RISKS**

Not applicable, no specific risks associated with participation in the HF have been identified. The risks to participants are the same as those encountered with the normal use of a SAGITTA® EVL R revision rod and associated postoperative follow-up.

#### **G. RATIONALE FOR THE BENEFIT/RISK BALANCE**

In accordance with the results of the clinical evaluation as well as those resulting from the risk management process applied to SAGITTA® EVL R revision rods, they benefit from minimized and acceptable risks in terms of the associated benefits when used in the context of their indication and in compliance with the instructions for use and recommendations issued by SERF.

The benefit/risk ratio is therefore favourable.

### **5. CI OBJECTIVES AND ASSUMPTIONS**

#### **A. CLAIMS AND PLANNED PERFORMANCE THAT NEED TO BE VERIFIED**

The following claims and performances will be considered during the CI:

- The implant survival rate/implant revision rate;
- Reduction of pain;
- Functional recovery of the hip joint

## B. EXPECTED RISKS AND ADVERSE EFFECTS THAT NEED TO BE ASSESSED

All the risks and expected adverse effects to be assessed during this CI are listed in the chapter 4.

All the complications observed will be listed in the patient's observation form.

Any effect, event, defect or malfunction that must be reported to the competent authorities will be reported in accordance with the provisions of Chapter 14.

## C. MAIN AND SECONDARY OBJECTIVES

### i. MAIN OBJECTIVE

The main objective of the HF is to study the survival rate, all causes of revision combined, of SAGITTA® EVL R revision femoral stems inserted between 01/01/2016 and 31/12/2018, in the medium term with a follow-up of at least 4 years postoperatively.

### ii. SECONDARY OBJECTIVES

The secondary objectives of this study are to:

- Study survival rates by components and etiology (revision and revision with reconstruction)
- Studying patient satisfaction with their hip prosthesis
- Confirm the safety of these implants by studying any complications observed
- Evaluate performance through the clinical scores of HARRIS (HHS) and forgotten prosthesis score (SHO-12) of femoral stems SAGITTA® EVL R.

The criteria for each of the objectives are presented in Chapter 6.A.iii.

## D. PRIMARY AND SECONDARY ASSUMPTIONS TO BE REJECTED OR ACCEPTED BASED ON CI STATISTICAL DATA

Not applicable, the objectives of this CI are descriptive.

## E. JUSTIFICATION OF PARAMETERS AND ASSUMPTIONS

Not applicable, the objectives of this CI are descriptive.

# 6. CLINICAL INVESTIGATION DESIGN

## A. GENERAL

### i. DESCRIPTION OF THE TYPE OF HF

This is a post-marketing clinical follow-up study performed in routine care with an additional non-heavy and non-invasive Cas 4.1, single-center, non-randomized, observational, non-comparative, ambispective, post-marketing procedure performed under normal conditions of use.

### ii. LIMITATIONS OF BIAS

The cohort of subjects included in the study represents a comprehensive and consecutive series of subjects.

The cohort will therefore make it possible to generate data in real-life conditions.

As the inclusions are retro-prospective, this can impact the quality of retrospective data collection.

### iii. PRIMARY AND SECONDARY OUTCOMES

The outcomes presented below were chosen in accordance with the HF objectives presented in Chapter 5C.

- Primary outcome:

The medium-term survival rate (minimum 4 years postoperatively) is defined via the Kaplan-Meier analysis, for all patients who still have the stem in place at the follow-up considered. Each inflection point will correspond to revision surgery with removal or change of the stem, all causes of revision combined.

- Secondary outcomes:

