Secondary outcome(s)	
The survival rate by component as well as the survival rate by etiology will be determined according to the Kaplan-Meier all-cause curve.
 
The safety of the implants will be evaluated by the occurrence of adverse events related to the medical device. These elements will be sought by the clinical examination of the practitioner and the radiological examination, carried out as part of routine practice.
 
Patient satisfaction with their hip replacement will be assessed using a satisfaction questionnaire.
 
Implant performance will be assessed through the Harris Clinical Hip Score (HHS) and Forgotten Hip Score (SHO-12).

Description of the study population	
Between January 2016 and December 2018, about 120 patients were operated on with a SAGITTA® EVL R revision femoral stem at the Rouen University Hospital – Charles Nicolle Hospital. All patients with a SAGITTA® EVL R revision femoral stem will be seen again at a medium-term postoperative follow-up visit (minimum 4 years postoperatively). During this follow-up, they will be offered to participate in this clinical investigation.

Criteria for Inclusion of Subjects	
 
- Patient of legal age on the date of surgery,
 
- Patient implanted with a SAGITTA® EVL R revision femoral stem as part of its indications between 01/01/2016 and 31/12/2018,
 
- Patient with a health insurance scheme
 

Criteria for non-inclusion of subjects	
 
- Patient who has not expressed consent to the collection of his/her data and participation in the study,
 
- Patient unable to understand the surgeon's instructions or perform postoperative follow-up.
 

	

- Patient with a contraindication to the use of the SAGITTA® EVL R revision femoral stem

- Patient implanted with a SAGITTA® EVL R revision femoral stem outside of their indication

Number of Subjects	As the study is descriptive, there is no calculation of the number of subjects needed according to a hypothesis. All patients operated on at the Rouen University Hospital – Charles Nicolle Hospital and with a SAGITTA® EVL R femoral stem will be included. This represents about 120 patients.

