**C. TOPICS**

**i. INCLUSION CRITERIA**

- Patient of legal age on the date of surgery,
- Patient implanted with a SAGITTA® EVL-R revision femoral stem in the context of its indications between 01/01/2016 and 31/12/2018,
- Patient benefiting from a health insurance scheme.

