### **Inclusion of subjects in the CI**

Patients scheduled for their usual follow-up visit will be selected (detailed process available in Chapter 13) and at the end of the screening process, the patient will be included if he or she consents to participate in the study.

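### The primary survival rate is worded for patients who still have the stem in place, which contradicts its own event definition and leaves room for upward bias

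*Protocol*

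**What the plan says.** Section 6.A.iii of the protocol states the primary survival rate "for all patients who still have the stem in place at the follow-up considered". It then defines the event: "Each inflection point will correspond to revision surgery with removal or change of the stem, all causes of revision combined". The secondary outcome on survival by component and etiology, in the same section, takes over the primary definition and applies it in subgroups.

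Other sections set the population by implantation. The main objective (5.C.i) is to "study the survival rate, all causes of revision combined, of SAGITTA® EVL R revision femoral stems inserted between 01/01/2016 and 31/12/2018". The inclusion criterion (6.C.i) requires a "revision femoral stem in the context of its indications between 01/01/2016 and 31/12/2018".

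On recall, the synopsis (description of the study population) says: "All patients with a SAGITTA® EVL R revision femoral stem will be seen again at a medium-term postoperative follow-up visit". Section 6.D.i, on inclusion of subjects, says: "Patients scheduled for their usual follow-up visit will be selected". The summary of the study in 6.D.i offers participation, at a routine consultation at least 4 years after surgery, to patients implanted in the period.

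**The concern.** A survival estimate needs a population fixed at time zero, here implantation, and then followed for the event. Section 6.A.iii describes the population by a status known only at follow-up, and that status is freedom from the event. Someone who builds the analysis set from 6.A.iii leaves out the failures. Someone who builds it from 5.C.i and 7.C.iii keeps them. One protocol thus supports two primary analyses.

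Any error runs one way. Omitting failed stems raises survival, in a study that the synopsis says will confirm the stem's performance and safety. Little else in the plan would expose it: sensitivity analyses are optional (7.J.ii) and there is no pass/fail criterion (7.G). Section 10.B treats a deviation on the primary outcome as major, so the text of that definition carries weight.

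This is a statement in the protocol that conflicts with its neighbours. It is not a detail that could properly be left to a statistical analysis plan.

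**Working it through.** **Passages side by side**

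- 6.A.iii, first sentence: patients with the stem still in place. Events possible in that set: none.
- 6.A.iii, second sentence: the curve steps at removal or change of the stem. This needs failed stems in the set.
- 5.C.i: all stems inserted 01/01/2016 to 31/12/2018, with no condition on current status.
- 6.C.i and 6.C.ii: inclusion rests on implantation, and non-inclusion does not bar a patient whose stem was removed.
- 7.C.ii: revision rate = revised patients / all patients included. For stem removals this would always be zero under the first sentence of 6.A.iii.
- 7.C.iii: D_i counts removals and changes, and censoring is for loss to follow-up, death or leaving the study.

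The first item cannot hold together with the others.

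**Possible size**

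The protocol derives no figure on this point (120 is a head count, and there is no precision target), so there is nothing to reproduce. The following is an illustration.

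Inputs: N = 120 (6.C.viii); reference revision rate 15.2% at 5 years (3.A). Assumptions: the benchmark applies to this stem, all 120 are included, nobody dies or is lost, and the hazard is constant. The share f of failed stems left out is not in the documents, so it is varied.

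- Hazard = −ln(1 − 0.152)/5 = 0.0330 per year.
- Revised by 5 years: 120 × 0.152 = 18.24.
- Revised by 4 years: 1 − 0.848^(4/5) = 12.4%, or 14.8 patients.
- Survival with share f left out: 1 − F(1 − f)/(N − fF), where F is the number revised.

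| f | Patients kept | Failures kept (5 y) | 5-year survival | 4-year survival |
|---|---|---|---|---|
| 0 | 120.0 | 18.2 | 84.8% | 87.6% |
| 0.25 | 115.4 | 13.7 | 88.1% | 90.4% |
| 0.50 | 110.9 | 9.1 | 91.8% | 93.4% |
| 0.75 | 106.3 | 4.6 | 95.7% | 96.6% |
| 1 | 101.8 | 0 | 100% | 100% |

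The two middle columns refer to 5 years. A Kaplan-Meier simulation with the same hazard and follow-up uniform between 4.1 and 7.4 years gave 84.8%, 88.0%, 91.7%, 95.6% and 100% at 5 years, in agreement with the counts.

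For scale, the Wald 95% half-width at 84.8% with n = 120 is 1.96 × √(0.152 × 0.848/120) = 6.4 points. Leaving out half of the failures shifts the estimate by 91.8 − 84.8 = 7.0 points, slightly more than that.

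**The case against.** The strongest reply is that the phrase is loose Kaplan-Meier language. Section 7.C.iii uses similar words for the number of subjects whose implant is in place at a given time, and 6.A.iii may only be describing who counts as surviving. The text is plainly a translation, so one clause should not carry much weight. The synopsis states the primary outcome without the condition, and 6.C.i, 6.C.viii, 7.B, 7.C.ii and 7.C.iii all need failed stems in the set. Complications since implantation are collected (6.A.iii, 6.A.iv), so a revision would be recorded for anyone enrolled. This stands as evidence of intent. It does not remove the contradiction from the definition of the only primary outcome.

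Three stronger readings are tempting and are not supported:

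- *Recall is restricted to current carriers.* In the synopsis, the sentence before the recall statement speaks of patients operated on with the stem, and the recall wording naturally refers back to them. Section 6.C.ix speaks of reconvening all patients, and the 6.D.i summary of patients implanted in the period. What remains is a gap: enrolment runs through a routine visit at 4 years or more, and no section says that a patient whose stem was removed or exchanged is called to it.
- *The reported survival will be 100%.* That is the literal extreme, and it conflicts with most of the protocol.
- *Failures will be hidden by a second study stem on the same femur.* Nothing in the documents shows that this occurs. It justifies a clarifying line and no more.

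**Conclusion.** The primary outcome definition contradicts itself and the sections around it, and should be corrected. The documents support no more than that: all implanted patients are probably meant, but the wording permits an analysis set chosen on the outcome, and the recall text does not close the gap.

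The direction of any resulting bias is certain: survival is overstated. Its size is not known. Under the assumptions above, five-year survival would move from 84.8% to about 88%, 92% or 96% for a quarter, half or three quarters of failures left out. These shares are illustrative. The 15.2% is a state-of-the-art figure and not this stem's own rate, and 6.D.iii expects many deaths and losses, so fewer than 120 patients will be analysed.

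**What to change.** 1. In 6.A.iii, replace the phrase with: *for all eligible patients implanted with a SAGITTA EVL R stem between 01/01/2016 and 31/12/2018, whether or not the stem is still in place*. State that time zero is implantation and that removal or change of that stem is the event. The secondary survival analyses then inherit the corrected definition.
2. In the synopsis and 6.D.i, state that the recall list is drawn from the centre's implant records for the window, irrespective of current stem status.
3. As a supporting clarification, state that the index stem is the first study stem on that femur in the window.

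The cost is a few lines of protocol text and slight extra work on the recall list. The reported survival may be less favourable.

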#### **Survival rates by components and etiology**

The definition is the same as for the primary outcome but with d in subgroups:

- According to the different implant assemblies
- As indicated revision or revision with reconstruction. The CCAM codes related to the intervention will allow this distinction.

#### **Satisfaction**

The satisfaction of the subjects will be evaluated through a graduated scale with 5 levels (Likert scale) with the following 5 response options:

- Very satisfied,
- Rather satisfied,
- Neither satisfied nor dissatisfied,
- Rather dissatisfied,
- Very dissatisfied.

#### **Complications**

All complications (events, adverse reactions and dysfunctions, serious or not, expected or not; see definitions in the chapter 0) observed since the implantation of the SAGITTA® EVL R rods for each subject will be identified, including those observed outside of the monitoring planned by this ICP.

Complications may also be grouped according to their etiology. In all cases, the causal link with the device under investigation will be studied.

#### **Functional Clinical Scores and Ratings**

- *Harris Hip Score*:

The Harris score (HHS) is one of the main functional clinical scores used after hip replacement surgery and evaluates 3 "items" relating to the diseased or operated hip:

- Pain (44 points)
- Function (47 points)
- Mobility (9 points)

For a maximum total score of 100 (minimum score:0), the HHS results will be categorized as follows:

 Harris WH. Traumatic arthritis of the hip after dislocation and acetabular fractures: treatment by mold arthroplasty. An end-result study using a new method of result evaluation. *J Bone Joint Surg Am.* 1969; 51: 737–55.

HHS	
Excellent	90-100
Good	80-89
Correct	70-79
Bad	< 70

The HHS fill grid is available in **Appendix 5**.

- *Forgotten Hip Score (FJS-12):*

The Forgotten Hip Score (SHO-12) is the French version of the FJS-12 (*Forgotten Joint Score*). The objective of this self-questionnaire is to estimate the degree of neglect of the hip and knee prosthesis through 12 questions.

Each item has 5 levels of response:      Never: 0 points

Almost never: 1 point  
Rarely: 2 points  
Sometimes: 3 points  
Often: 4 points

The sum of the items is divided by the number of items and multiplied by 25 to obtain a score out of 100.

The OHSS Fill Grid is available in **Appendix 6**.

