### C. ANALYTICAL PROCEDURES

#### i. CALCULATION OF CONFIDENCE INTERVALS

All confidence intervals will be calculated at 95%, i.e.:  $z_{\frac{\alpha}{2}} = 1.96$

The confidence intervals for discrete qualitative and quantitative variables will be calculated using the following formula:

$$IC_{95} = \left[ p - z_{\frac{\alpha}{2}} \times \sqrt{\frac{p \times (1-p)}{n}} ; p + z_{\frac{\alpha}{2}} \times \sqrt{\frac{p \times (1-p)}{n}} \right]$$

With:

- $IC_{95}$ , the 95% confidence interval
- p, the proportion observed;
- $z_{\frac{\alpha}{2}} = 1.96$ , the value derived from the normal distribution for a risk  $\alpha$  5%;
- n, the sample size.

The confidence intervals for the means of the continuous quantitative variables will be calculated using the following formula:

$$IC_{95} = \left[ m - z_{\frac{\alpha}{2}} \times \frac{\sigma}{\sqrt{n}} ; m + z_{\frac{\alpha}{2}} \times \frac{\sigma}{\sqrt{n}} \right]$$

With:

- $IC_{95}$ , the 95% confidence interval
- $m$ , the observed mean;
- $\sigma$ , the standard deviation observed
- $z_{\frac{\alpha}{2}} = 1.96$ , the value derived from the normal distribution for a risk  $\alpha$  5%;
- $n$ , the sample size.

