**8. DATA MANAGEMENT**

**A. DATA ENTRY AND COLLECTION METHODS**

The data will be collected from the patient records in the paper CRF directly by the investigator. The CRF data will then be entered into a database by a representative of the sponsor.

In accordance with applicable laws and regulations, data confidentiality will be ensured by appropriate security means:

- Patients will be identified in the CRF and the clinical database by a numerical identifier combining the number of the center and the number of the patient. Only the centres will keep a confidential list of included patients that will link the patient's ID to their identity.
- No personal data will be collected.

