**APPENDIX 6: FORGOTTEN HIP SCORE – SHO12**

Are you aware of your hip...	1pt	2pts	3pts	4pts	5pts
	Never	Hardly ever	Rarely	Sometimes	Often
1. ... in your bed at night?					
2. ... When you sit in a chair for more than an hour?					
3. ... When you walk for more than 15 minutes?					
4. ... when you take a bath or shower?					
5. ... When you travel by car?					
6. ... When you climb the steps of a staircase?					
7. ... When you walk on uneven ground?					
8. ... When you get up from a low sitting position?					
9. ... When you stand for a long time?					
10.... When you do housework or gardening?					
11.... When you are walking or hiking?					
12.... when you practice your favorite sport?					
12b... during your sexual intercourse?					

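### The Appendix 6 form prints 1 to 5 points for SHO-12 responses that section 6.A.iii codes 0 to 4; if the printed points go into the stated formula, every score is 25 points too high

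*Protocol*

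**What the plan says.** Section 6.A.iii (Functional Clinical Scores and Ratings) describes the SHO-12 as a self-questionnaire of 12 questions with five response levels. The points run in steps of one from "Never: 0 points" to "Often: 4 points". The scoring rule follows: "The sum of the items is divided by the number of items and multiplied by 25 to obtain a score out of 100". The reader is then sent to the form: "The OHSS Fill Grid is available in" Appendix 6.

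Appendix 6 lists the same five responses in the same order, *Never* to *Often* (the second label is worded slightly differently). Above them it prints 1, 2, 3, 4 and 5 points. It has no formula, no total line and no instruction to subtract 1. It prints 13 rows: 1 to 12, plus "12b... during your sexual intercourse".

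Section 6.D.i (Follow-up visits) says that the investigator collects the SHO-12 with the Appendix 6 questionnaire. Section 8.A describes a paper CRF and adds: "The CRF data will then be entered into a database by a representative of the sponsor".

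Section 5.C.ii names the SHO-12, with the Harris Hip Score, as a measure for the secondary performance objective.

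**The concern.** The Protocol gives two point codings for one questionnaire, and only one fits its own formula. The coding that does not fit is printed on the form used at the visit, directly above the boxes to be ticked. Anyone who totals the form as printed and then applies the formula gets a score on the wrong range.

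The error would be hard to see. A range check finds only scores above 100. A patient whose average response is *Sometimes* or lower would get 25 to 100, which looks valid but is 25 points too high.

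Nor would it cancel. The schedule in section 6.A.iv excludes the SHO-12 from the preoperative assessment, so there is no within-patient change in which a constant offset would disappear. The follow-up level is itself the SHO-12 result.

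**Working it through.** **Inputs**

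- Item codes in section 6.A.iii: 0, 1, 2, 3, 4.
- Item points printed in Appendix 6: 1, 2, 3, 4, 5, over the same ordered responses.
- Formula in section 6.A.iii: score = (sum of items ÷ number of items) × 25.
- Number of items in section 6.A.iii: 12.

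**Step 1: reproduce the stated range.** With codes 0–4 and 12 items the sum runs from 0 to 48. The minimum is 0/12 × 25 = 0 and the maximum is 48/12 × 25 = 100. This agrees with the stated 100-point score.

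**Step 2: put the printed points into the same formula.** The sum runs from 12 to 60. The minimum is 12/12 × 25 = 25 and the maximum is 60/12 × 25 = 125.

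| All items answered | Section 6.A.iii coding | Appendix 6 points | Difference |
|---|---|---|---|
| *Never* | 25 × 0 = 0 | 25 × 1 = 25 | +25 |
| *Rarely* | 25 × 2 = 50 | 25 × 3 = 75 | +25 |
| *Sometimes* | 25 × 3 = 75 | 25 × 4 = 100 | +25 |
| *Often* | 25 × 4 = 100 | 25 × 5 = 125 | +25 |

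**Step 3: any mixture of responses.** Let S be the sum on the 0–4 coding over k items. The printed points give S + k, so the difference is ((S + k)/k − S/k) × 25 = (k/k) × 25 = 25. It depends neither on the pattern of answers nor on k, as long as the divisor is the number of items summed. A check on 100,000 random response patterns with 1 to 13 items gave 25.0 every time.

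**Step 4: effect on the reported summaries.** Section 7.C.i gives the interval for a mean as m ± 1.96 × SD/√n. Adding 25 to every score leaves the SD unchanged, so the interval becomes (m + 25) ± 1.96 × SD/√n. Both limits rise by 25 and the width stays the same. The median, minimum and maximum, which section 7.B also asks for, rise by 25 too.

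**Step 5: how far the figure depends on the reading of the formula.**

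- *Divisor fixed at 12.* The shift would be 25k/12: 18.75 with 9 items answered, 22.92 with 11, 25.0 with 12, and 27.08 if all 13 printed rows were summed.
- *Score reversed as 100 minus the result.* The 0–4 coding still gives 0 to 100. The printed points would give 100 − 125 = −25 to 100 − 25 = 75, so scores would be 25 too low.
- *Row count under the 0–4 coding.* Thirteen rows with divisor 13 keep the range 0–100. Thirteen rows with divisor 12 have a maximum of 52/12 × 25 = 108.3.

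**The case against.** The best defence is that section 6.A.iii is complete and coherent. It names each response, gives its points, and states the formula and the range. An analyst who follows it gets 0–100. Appendix 6 holds no scoring rule, so an error requires someone to set the written coding aside and use the column labels. The CRF pages, database specification and any SAP are not at hand, and whether the ticked response or the printed value is keyed is the kind of detail often settled there.

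This rightly makes the error conditional, and silence on data entry is not a fault in itself. The contradiction remains, because the Protocol itself fixes the coding, the formula and the form, and they disagree. A conversion written elsewhere would protect the analysis but leave the visit form in conflict with the text.

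A second objection is that +25 rests on an unreversed score and on a divisor equal to the number of items summed. Both conditions are real. Both are also the plain reading of the formula, which contains no reversal and divides by the number of items.

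A third is that little depends on the score. Section 6.A.iii gives the SHO-12 no categories or cut-offs, and section 7.G sets no success criterion. That is correct, and it limits the importance of the point.

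**Conclusion.** The point holds. The Appendix 6 points cannot enter the section 6.A.iii formula unconverted and yield a 100-point score; the 0–4 coding can. If the printed points are used, with divisor equal to the items summed and no reversal, every patient's score, the mean and both confidence limits are 25 points too high.

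The consequence is confined to the level of one secondary descriptive outcome. The SD, the interval width and the primary survival outcome are unaffected, and no information is lost because the ticked responses remain on the form. It should be corrected because it is a wrong value on the instrument for a named secondary outcome and is easy to miss in the data.

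**What to change.** Do one of the following:

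- print 0, 1, 2, 3, 4 above the response columns in Appendix 6; or
- keep the form and state in section 6.A.iii, before the formula, that 1 is subtracted from each printed value.

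Two optional sentences could go into the same edit:

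- *Direction.* As coded, a higher score means more awareness of the hip. That is opposite in sense to the purpose given in section 6.A.iii (how far the joint is forgotten) and to the Harris Hip Score, where higher is better. Say so, or state the reversal if one is intended.
- *Rows 12 and 12b.* State how they count in the sum and in the divisor, given that the text speaks of 12 questions and the form has 13 rows.

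The cost is one header line (or one sentence) plus up to two sentences. No new data are needed, and forms already completed can be rescored exactly from the ticked boxes.
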